### **Analysis Plan**

Overview: We will use an unadjusted difference-in-differences analytic approach to testing comparative effectiveness hypotheses, weighting for differences in cluster size. Despite expected between-clinic differences in baseline characteristics and BP control (especially in the non-randomized comparison with Usual Care control organizations), the difference-in-differences approach provides some protection against confounding because the outcome being compared is a within-clinic change score, as described below. We will first conduct 3 pairwise primary hypothesis tests (adjusting for multiple comparisons), as described below. We will then conduct a series of exploratory analyses of secondary outcomes, sensitivity analyses adjusting for baseline clinic-level characteristics, subgroup analyses to examine heterogeneity of effect, and exploratory mediation analyses to understand the mechanisms by which the full-support intervention might provide greater effectiveness.

Differences-in-differences analytic approach: We will calculate difference-in-differences through the following steps:

1. Use clinic-level metrics (e.g., % BP control) at baseline for each clinic before the intervention starts ( $t_0$ ) and then including the 6th full month of the intervention (" $t_6$ ", noting that the period will actually be 7 months offset for the Intervention Clinics and 6 months for the Usual Care Clinics; see Outcomes and Measurements, above)
2. Calculate the clinic-level pre-post difference in the metric ( $t_6 - t_0$ )
3. Calculate the mean pre-post difference in each treatment group, the between-group difference of differences, both with 95% confidence intervals, and compare the 20-28 pre-post differences by arm using weighted linear regression; observations will be weighted by the inverse of the site-specific variances of the change scores, which will be approximated using the site-specific sample size and level of the time-specific metrics, and the average correlation of the pre- and post-metrics across clinics. Weights will be normalized to sum to the total number of clinics in the Arm 1 vs. Arm 2 comparisons (and to the number of included clinics plus the number of participating PCORnet datamarts for the comparisons of each Arm with Usual Care).

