### Primary hypothesis tests, with adjustment for multiple comparisons

Our primary hypothesis tests will be 3 pairwise comparisons:

- Test 1: Arm 1 vs Arm 2
- Test 2: Arm 1 vs. Usual Care
- Test 3: Arm 2 vs. Usual Care

In order to maintain an overall type 1 error rate of 5%, we will set our critical p-value threshold for Test 1 at  $p=0.04$ , and then at  $p=0.005$  for Test 2 and Test 3 since they will benefit from the very large sample size expected in the Usual Care groups. No other adjustments for multiple comparisons are planned for secondary outcomes or other exploratory analyses described below.

**Descriptive analyses comparing clinic-level baseline characteristics:** *Descriptive statistics* will be used to compare clinic-level characteristics between the two intervention arms at baseline. We will include descriptions of clinic-level patient population characteristics (age groups, gender, race/ethnicity, type of insurance, mean number of current antihypertensive medication classes prescribed, and prevalence of comorbid conditions such as diabetes, chronic kidney disease, or heart failure), workforce composition (i.e. proportion of nurse practitioners, physician assistants, physicians, and physician specialty - internal vs family medicine), clinic size and staffing level (total number of patients, nurses, and medical assistants), level of access (availability of same-day appointments, mean time to third next available appointment), and possibly other characteristics depending on availability.

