**Sensitivity analyses:** In a sensitivity analysis, we will perform multivariable linear regression analyses to compare clinic-level pre-post differences in our primary and secondary outcomes. The regression models will adjust for health system as well as for whether the clinic was engaged in BP HOME, a concurrently running individual-level randomized trial that will provide home blood pressure monitoring devices to participating patients with a high blood pressure reading in clinic. We will also consider linear mixed models (LMMs) for repeated changes in the summary outcome measures, adjusting for age, sex and race-ethnicity. In particular, for each clinic we will calculate monthly values of the metric  $(t_i - t_0)$ , for follow-up month  $i = 1, \dots, 6$ , within strata jointly defined by age, sex, and race-ethnicity, as well as corresponding within-stratum weights as described above, then estimate the effect of treatment adjusted for stratum, using an LMM that includes treatment assignment, month as categorical, the interaction of these two factors, and stratum. With a view towards model simplification, likelihood ratio testing will be used to determine whether age, sex, and race/ethnicity as additive factors adequately capture the stratification effects. We will: (1) present month-specific treatment effects with 95% confidence intervals (CIs); (2) test for heterogeneity in the monthly treatment effects across months; (3) summarize the treatment effect by the average of the month-specific effects also with a 95% CI, if the test for heterogeneity is not statistically significant ( $P>0.05$ ); and (4) otherwise, use orthogonal contrasts to check for linear and quadratic trends in the monthly effects.

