**Data source, collection, management, and safety:** Consistent with principles of pragmatic clinical trials, we will use EHR data for patient identification and assessment of intervention implementation and outcomes. Both interventions (and usual care) are consistent with standard of care. Therefore, both the interventions and data collection in this study carry minimal risk to patients. We will leverage the data infrastructure and resources in the PCORnet Common Data Model to collect de-identified, clinic-level aggregate data needed for analysis. Additional details on the PCORnet Common Data Model procedures for data collection and linkage, and data management and safety are described elsewhere.

**Sample size and power:** Preliminary data from “Wave 2” implementation of the M.A.P. Program by AMA in 16 clinics shows average pre-post improvements (without a control group) in BP control of 6.8% (65.6%-->72.4% overall) +/- 4.4% (standard deviation of change in control rate). Assuming negligible change in the Self-Guided arm, standard sample size calculations show that we will have 83% power to detect a difference in differences of 6% in the BP control rate (or 92% power for 7% difference) between Self-Guided and Full-Support arms with 10 clinics randomized to each arm of the study; these results were confirmed using simulations. Power will be higher for comparisons of the Self-Guided and Full-Support groups with the large Usual Care comparison group in PCORnet under similar effect-size

assumptions. For the HTE analysis comparing the difference in differences between the 10 clinics in CDRN 1 (5:5 in each arm) and the 10 clinics in CDRN 2 (5:5 in each arm), we expect to have 80% power to detect an interaction effect (i.e., the difference in the difference in differences) of 12% in the BP control rate. Corresponding minimum detectable interaction effects would be 15%, 13%, and 12% for demographic subgroups comprising 20%, 30%, and 40% of the overall population.

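### Test 1 compares clinic change scores without conditioning on baseline % BP control; this is valid, but may cost precision, and one added covariate would address it

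*Combined protocol and SAP*

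**What the plan says.** The Analysis Plan overview sets the method for all three primary tests: "We will use an unadjusted difference-in-differences analytic approach to testing comparative effectiveness hypotheses, weighting for differences in cluster size". The steps that follow take the difference t6 - t0 for each clinic and then "compare the 20-28 pre-post differences by arm using weighted linear regression". No covariate is named. Baseline % control therefore enters Test 1 by subtraction and, through the level of the metric, in the weights. The weights also use "the average correlation of the pre- and post-metrics across clinics", for which no value is given.

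The stated reason for the approach is that it "provides some protection against confounding because the outcome being compared is a within-clinic change score". The overview offers this especially for the non-randomised comparison with Usual Care.

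The overview also announces "sensitivity analyses adjusting for baseline clinic-level characteristics". The Sensitivity analyses paragraph then lists what these contain: "The regression models will adjust for health system as well as for whether the clinic was engaged in BP HOME". Its mixed model for monthly changes adds strata of age, sex and race-ethnicity. Baseline % BP control is not named in either. Under Randomization, the stratification factors are CDRN and BP HOME participation.

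**The concern.** Test 1 is the only randomised comparison among the three primary tests, and it has 20 to 28 units. A change score assumes that a clinic starting one point higher will end one point higher. If the true slope is below 1, clinics that start low tend to gain more than clinics that start high, whatever their arm. The arm that happens to start lower then shows a somewhat larger gain with no treatment effect. A model containing t0 estimates the slope instead of fixing it, and t0 is already in hand for every clinic. If the covariate matters and is not prespecified, adding it after an imbalance has been seen would be a post hoc choice.

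**Working it through.** **Inputs from the plan.** SD of clinic change 4.4 points, 10 clinics per arm, and stated power of 83% for 6 points and 92% for 7 points (Sample size and power). Threshold for Test 1 p = 0.04 (Primary hypothesis tests). 10-14 clinics per arm (Randomization). In the worked example, two 12-month windows offset by 7 months (Outcomes and measurements).

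**Assumptions.** Two-sided tests, equal pre and post SDs across clinics, a linear relation and equal weights. The plan gives neither r nor the between-clinic SD, so r is varied.

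**The plan's own figure.** The standard error of the unadjusted difference is 4.4 x sqrt(2/10) = 1.97 points. A two-sided t-test at alpha 0.05 gives 82.2% power for 6 points and 92.0% for 7, which reproduces the stated 83% and 92%. At the Test 1 threshold of 0.04 the t-test gives 79.2% and 90.1%. (The normal approximation at 0.04 gives 84.0% and 93.4%, also within 2 points of the stated figures.) The 79.2% is the reference below. With 14 per arm it becomes 92.0%.

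**Effect of adding t0.**
- With SD0 the between-clinic baseline SD, the change variance is 4.4² = 2 x SD0² x (1 - r), so r = 1 - 4.4²/(2 x SD0²).
- Adjusting for t0 multiplies the variance by (1 + r)/2. Estimating the slope costs a factor 1 + 1/(2n - 4) and one degree of freedom. At n = 10 that factor is 1.0625.
- The unadjusted estimate moves by -(1 - r) points for each point of baseline difference between arms.

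| r | implied SD0 | net variance ratio, 10 per arm | adjusted power, 10 per arm (79.2% unadjusted) | adjusted power, 14 per arm (92.0% unadjusted) | shift in unadjusted estimate for a 5-point imbalance |
|---|---|---|---|---|---|
| 0.3 | 3.7 | 0.69 | 91.4% | 98.4% | 3.5 |
| 0.5 | 4.4 | 0.80 | 87.4% | 96.8% | 2.5 |
| 0.7 | 5.7 | 0.90 | 83.5% | 94.7% | 1.5 |
| 0.8 | 7.0 | 0.96 | 81.0% | 93.3% | 1.0 |
| 0.9 | 9.8 | 1.01 | 78.7% | 92.0% | 0.5 |
| 0.95 | 13.9 | 1.04 | 77.3% | 91.7% | 0.25 |

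Adjusted power is for a 6-point effect at alpha 0.04, from 20,000 simulated trials per scenario; the formulas above agree to within about 0.5 point.

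**Break-even.** Setting (1 + r)/2 x 17/16 = 1 gives r = 32/17 - 1 = 0.88 at 10 per arm, or SD0 = 4.4/sqrt(2 x 0.118) = about 9 points. At 14 per arm, (1 + r)/2 x 25/24 = 1 gives r = 0.92.

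**Imbalance and imprecision are the same quantity.** At r = 0.5 and 10 per arm, a baseline difference of one standard error is 4.4 x sqrt(0.2) = 1.97 points and moves the estimate by 0.5 x 1.97 = 0.98. As a share of the estimate's variance this is (0.98/1.97)² = 0.25, which equals (1 - r)/2, the share that adjustment removes before its small-sample cost. The unadjusted confidence interval already contains it.

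**Type I error.** In simulation under no effect, rejection was about 4% at 14 per arm with r = 0.9 for both analyses, as intended.

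**The case against.** The strongest reply is that nothing here is an error. The hypothesis concerns a larger increase from baseline, the primary outcome is defined as a change, and randomisation makes the change-score comparison unbiased with the intended type I error. That stands. A reader might infer that Test 1 is biased or invalid, and the documents do not support that. The dependence on chance imbalance is conditional on the allocation drawn, and it averages out over randomisation.

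A reader might also infer that the plan certainly loses power. That is not supported either, because r is not given. Some cues point towards the upper part of the range, where little is gained: the plan expects clinics to differ in baseline BP control, and the example windows share 12 - 7 = 5 months. Neither fixes r. Because the metric takes each patient's most recent reading, shared months need not mean shared readings.

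Nor is it right that baseline is ignored, since it is subtracted and its level enters the weights. Neither use estimates the slope, however.

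The overview's promise to adjust for baseline clinic-level characteristics could be read as covering baseline control. The paragraph that carries out the promise lists its covariates and does not include it.

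Finally, the calculation is unweighted, while the plan's weights are built for change-score variances and not for residual variance given t0. That is a fair limit on the exact figures.

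**Conclusion.** The point holds as a recommended improvement to a valid analysis. No listed model conditions on baseline % BP control, and the stratification does not use it. At 10 clinics per arm, adding it would cut the variance by about 20% at r = 0.5 and 10% at r = 0.7, by about 4% at r = 0.8, and not at all near r = 0.9. In power for a 6-point effect, the range runs from a gain of about 12 points (r = 0.3) to a loss of about 2 (r = 0.95), so the trade is favourable unless r is above about 0.88. Precision and chance imbalance should be counted once, since they are two views of the same variance. The sizes rest on the pilot SD of 4.4, equal pre and post SDs, two-sided alpha 0.04 and no weighting.

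**What to change.** For Test 1, prespecify as primary the weighted linear regression of t6 - t0 on arm plus baseline % BP control (centred), and keep the unadjusted difference-in-differences as a sensitivity analysis. If the sponsor prefers to keep the unadjusted test as primary, name baseline % control as a covariate in the Sensitivity analyses paragraph. That is the minimum needed to carry out what the overview announces.

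Leave Tests 2 and 3 as change scores, because those groups are not randomised. Extending the adjustment to the exploratory secondary metrics, each with its own baseline, is optional.

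The cost is one sentence, no new data and one degree of freedom. The primary tests would then use two different models, which the text should explain. If r exceeds about 0.88 at 10 per arm (baseline SD above about 9 points), there is no gain, or a loss of up to about 2 points of power over the range examined. The 5-month overlap of the measurement windows makes a high r more plausible, so the sponsor should check r in any pilot or pre-launch clinic data before fixing the model.

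### The primary between-group differences are to carry 95% intervals although Tests 2 and 3 are judged at p=0.005, so an interval can exclude zero beside a primary test that fails

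*Combined protocol and SAP*

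**What the plan says.** In the combined protocol and SAP, step 3 of the difference-in-differences approach (Analysis Plan) fixes the interval level: "Calculate the mean pre-post difference in each treatment group, the between-group difference of differences, both with 95% confidence intervals". The same step sets the weights for the arm-to-arm comparison and for each arm against Usual Care, so the 95% level covers all three contrasts.

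The section on primary hypothesis tests then states: "Our primary hypothesis tests will be 3 pairwise comparisons". Its aim reads "In order to maintain an overall type 1 error rate of 5" percent, and the alpha is divided accordingly: "threshold for Test 1 at $p=0.04$ , and then at $p=0.005$ for Test 2 and Test 3".

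It closes with "No other adjustments for multiple comparisons are planned for secondary outcomes or other exploratory analyses described below". That sentence concerns secondary and exploratory results, so it does not explain the level of the primary intervals. Nothing in the document gives an interval matched to the thresholds, says how a 95% interval should be read beside them, or calls the intervals descriptive.

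**The concern.** A two-sided 95% interval excludes zero exactly when p<0.05. If the test beside it is judged at a stricter level, there is a range of results in which the interval looks positive and the test has failed. For Tests 2 and 3 that range runs from p=0.005 up to p=0.05.

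These are the two non-randomized comparisons. The plan itself expects baseline differences to be most marked there, and it chose a strict threshold for them because the Usual Care sample should be very large. Many readers treat an interval that excludes zero as a positive finding. An arm-versus-Usual-Care result that fails its primary test could then be read as an effect, and the protection that the alpha split was meant to give would be lost in the reporting.

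**Working it through.** **Inputs from the document.** Thresholds 0.04, 0.005 and 0.005, and an overall error of 5% (primary hypothesis tests). Interval level 95% (Analysis Plan, step 3). SD of clinic-level change 4.4 points, 10 clinics per arm, and planning differences of 6 and 7 points (sample size and power paragraph). The design allows 10 to 14 clinics per arm.

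**Assumptions, because the document is silent.** Tests are two-sided. The number of Usual Care datamarts is taken as 10 to 60, and their SD of change as 4.4. The planned weighting is ignored.

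**1. The plan's own figure.** 0.04 + 0.005 + 0.005 = 0.05. Treating the tests as independent gives 1 - 0.96 × 0.995 × 0.995 = 0.0496. The stated 5% is reproduced.

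**2. Matching interval levels.** 1 - 0.04 = 96% for Test 1 and 1 - 0.005 = 99.5% for Tests 2 and 3. Ratios of normal quantiles to the 95% quantile:
- 96%: 2.054/1.960 = 1.05
- 99.5%: 2.807/1.960 = 1.43

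With t quantiles at 18 df the ratios are 2.214/2.101 = 1.05 and 3.197/2.101 = 1.52.

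**3. Test 1.** With 10 clinics per arm, SE = 4.4 × √(2/10) = 1.968. Half-width is 2.101 × 1.968 = 4.13 points at 95% and 2.214 × 1.968 = 4.36 at 96%. Only an observed difference between 4.13 and 4.36 points makes interval and test disagree. With 14 per arm the zone is 3.42 to 3.60. The chance is 0.05 - 0.04 = 1% with no true difference. At a true difference of 6 points it is power at 0.05 less power at 0.04: 82.2% - 79.2% = 3.0% (10 per arm).

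**4. Tests 2 and 3, no true difference.** Chance of disagreement per test = 0.05 - 0.005 = 4.5%.

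**5. Tests 2 and 3, true difference d.** With K datamarts and 10 clinics, SE = 4.4 × √(1/10 + 1/K). The chance of disagreement is power at 0.05 minus power at 0.005, from the non-central t with 10 + K - 2 df and non-centrality d/SE. For K=20 and d=6 this is 0.925 - 0.679 = 0.246.

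| Datamarts (assumed) | Half-width 95% | Half-width 99.5% | Ratio | Disagreement, d=3 | Disagreement, d=6 |
|---|---|---|---|---|---|
| 10 | 4.13 | 6.29 | 1.52 | 22.9% | 35.7% |
| 20 | 3.49 | 5.19 | 1.49 | 27.6% | 24.6% |
| 30 | 3.25 | 4.79 | 1.47 | 29.4% | 18.5% |
| 60 | 3.00 | 4.36 | 1.45 | 31.1% | 11.8% |

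With 20 datamarts, any observed difference from 3.49 up to 5.19 points gives a 95% interval excluding zero beside a failed test.

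**6. Limit of negligible Usual Care error.** SE = 4.4/√10 = 1.391 and d/SE = 6/1.391 = 4.31. Ignoring the far tail, disagreement = Φ(4.31 - 1.960) - Φ(4.31 - 2.807) = 0.991 - 0.934 = about 6%. With 14 clinics it is about 1%.

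**7. The three intervals together.** The Bonferroni bound is 3 × 0.05 = 15%, and independence would give 1 - 0.95³ = 14.3%. The contrasts share groups, so the joint error was simulated under no true differences (100,000 runs, unweighted t-tests, equal variances, 10 clinics per arm, and 10, 30 or 60 datamarts). At least one 95% interval missed zero in 12.3%, 12.1% and 12.0% of runs. The planned thresholds rejected at least once in 4.6%, 4.5% and 4.6%.

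**The case against.** The strongest reply is that no decision changes. The plan decides by p-value thresholds alone ("we will set our critical p-value threshold for Test 1 at" and so on), and no primary conclusion rests on whether an interval excludes zero. The plan promises control of test error; it does not promise joint coverage of intervals. This stands. A reader might infer that the 5% overall error is lost, or that the decision rule is broken. The documents do not support that: the thresholds add to 5%, and the simulation gives about 4.6%.

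A reader might also take 15% as the joint error of the three intervals. That is a ceiling which these contrasts do not reach, because any one is the difference of the other two; about 12% is the realistic figure.

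The size also depends on unstated quantities. True differences of 2 to 4 points with no Usual Care error give disagreement of 22-32% with 10 clinics, but the document does not plan on such effects. It plans on 6 to 7 points for Full Support vs Self-Guided and says the Usual Care comparisons assume similar effects. If Self-Guided and Usual Care both change negligibly, Test 2 sits at 4.5%. No single percentage is therefore robust. The range still includes values large enough to matter: 12-36% at 6 points once Usual Care error is counted.

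Finally, the randomized comparison, which is the main aim, is barely touched. That is right, and the case rests on Tests 2 and 3.

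**Conclusion.** The mismatch is real, and nothing in the document resolves it. It is an inconsistency between reported intervals and tests, and type 1 error control by the p-values is unaffected. It is trivial for Test 1 and material for the non-randomized Tests 2 and 3, where the matching interval is 43-52% wider than the planned one. For each of those two tests, the chance of a contradictory result runs from 4.5% with no true difference to about a third in unfavourable settings, and it falls to about 6% or less at 6 points if Usual Care error is negligible. These figures rest on two-sided tests, an SD of 4.4 carried over to Usual Care where its error is counted, an assumed datamart count and no weighting. The existence of the mismatch needs only the two-sided assumption. It should be corrected before analysis, but it does not put the design or the tests in doubt.

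**What to change.** Add one sentence to step 3 or to the section on primary hypothesis tests. For the 6-month primary outcome, the between-group difference is reported with a 96% interval for Test 1 and 99.5% intervals for Tests 2 and 3. Non-coverage then sums to 0.04 + 0.005 + 0.005 = 0.05, and interval and test always agree. Keep 95% intervals for within-group changes and for secondary and exploratory results, labelled as unadjusted for multiplicity.

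If 95% intervals are also shown for the primary contrasts, state that primary conclusions follow the p-value thresholds.

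The cost is wider, less precise-looking intervals for Tests 2 and 3, and about 5% more width for Test 1. Data, randomization, sample size and tests stay as they are.

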**Table 3. Subgroups for HTE analysis**

Age: 18-44 vs. 45-64 vs. 65+

Race/ethnicity: NH White vs. NH Black vs. NH Asian vs. Hispanic (any race) vs. Other
Sex: Male vs. Female
Enrolling CDRN
HTE – Heterogeneity of treatment effects
NH – Non-Hispanic

**Exploratory Mediation analysis:** As many of our secondary outcomes are presumably process measures in the causal pathway to achieving BP control, we will perform a mediation analysis to understand the degree to which the potential added benefit of the Full Support intervention on BP control is explained by changes in the process measures. We will perform a mediation analysis using nested linear regression models for the effect of randomization assignment (i.e. Full Support vs. Self-Guided) on clinic level pre-post differences in percent control, first omitting, then adding each of our proposed mediators to the base model. The hypothesized process mediators will include pre-post changes in BP measurement accuracy, medication intensification, and average SBP reduction after medication intensification, and repeat visit in 4 weeks after uncontrolled HTN. These analyses will be implemented using the Paramed module in Stata statistical software  to calculate natural direct effect (NDE) of full-support on BP control and the natural indirect effect (NIE) through each mediator. The total causal effect (TCE) is the sum of the NDE and NIE. Dividing each NIE by the TCE will calculate the proportion of the causal effect explained by each mediator.

**Additional exploratory analyses:** We will explore temporal patterns in the effect of randomization assignment using linear mixed models for repeated clinic-level changes since baseline in primary and secondary outcomes assessed at 6, 12, and 18 months. These models will include random effects for clinic, as well as fixed effects for treatment assignment (as a categorical variable), and their interaction. Heterogeneity of treatment effects across time will be tested using a 2 degree-of-freedom chi-square test; in addition, a chi-square test for linear trend will be obtained by comparing the fitted treatment assignment effects at 6 and 18 months.

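### Change-score weights use each site's own follow-up level: negligible for the primary outcome, possible bias for low-level process metrics, and infinite weights in the stratified sensitivity model

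*Combined protocol and SAP*

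**What the plan says.** The Analysis Plan overview gives the purpose as "weighting for differences in cluster size". Step 3 then specifies more than size: "observations will be weighted by the inverse of the site-specific variances of the change scores". Those variances are "approximated using the site-specific sample size and level of the time-specific metrics", together with "the average correlation of the pre- and post-metrics across clinics". The time-specific levels are those at t0 and t6. No formula and no value for the correlation is given.

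The Sensitivity analyses paragraph adds a further model: "We will also consider linear mixed models (LMMs) for repeated changes in the summary outcome measures". Monthly changes from baseline, months 1 to 6, are to be computed "within strata jointly defined by age, sex, and race-ethnicity, as well as corresponding within-stratum weights as described above". That paragraph does not define the strata. The only categories in the document are those of Table 3: "Age: 18-44 vs. 45-64 vs. 65" and over for age, two sexes, and "NH White vs. NH Black vs. NH Asian vs. Hispanic (any race) vs. Other" for race/ethnicity.

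The plan has no floor, smoothing, pooling, minimum cell size, or rule for cells that are empty or at 0% or 100%.

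**The concern.** For a percentage, the natural reading of step 3 puts p(1-p) at follow-up into the weight, so the weight is a function of the outcome being averaged. Below 50%, a clinic whose metric rises gets a larger estimated variance and a smaller weight. Above 50%, the reverse holds. If clinic-to-clinic variation in change differs between arms, the two arm means shift by different amounts and the difference in differences is biased.

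In small strata the same formula can return a variance of exactly zero. The weight is then 1/0, and weights that must be normalized to a fixed sum do not exist. The analyst would have to choose a floor or drop cells after seeing the data.

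**Working it through.** **The plan's own figures.** No stated figure involves the weights. The nearest is the power statement (83% for 6 points and 92% for 7, 10 clinics per arm, SD 4.4). A two-sample t test with 18 df and two-sided alpha 0.05 gives 82.2% and 92.0%. That calculation is unweighted, so it does not bear on this point.

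**Formula used** (inferred from step 3, since none is written): Var = v0 + v6 - 2r√(v0·v6), with v = p(1-p)/n at each time and weight = 1/Var. The correlation r is assumed between 0 and 0.7.

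**1. How the outcome enters the weight.** Assume equal n, baseline 10%, and half the Full Support clinics rising to 25% while the rest stay put. Multiplying each variance by n:
- r = 0: responders 0.09 + 0.1875 = 0.2775; non-responders 0.09 + 0.09 = 0.18. Relative weight 0.18/0.2775 = 0.65. Weighted mean change 15 × 0.65/1.65 = 5.9 points, against a true 7.5 (-21%).
- r = 0.7: responders 0.2775 - 1.4 × √(0.09 × 0.1875) = 0.0956; non-responders 0.18 - 1.4 × 0.09 = 0.054. Relative weight 0.56. Weighted mean 5.4 points (-28%).

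**2. Effect on the difference in differences** (simulation, 10 clinics per arm, 1,000 patients per clinic, r = 0.3, 6,000 trials; baseline 10% and all SDs of change assumed):

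| True rise, Full Support | SD of change, Full Support / Self-Guided | Weighted v true |
|---|---|---|
| 20 points | 12 / 0 | 17.7 v 20.1 |
| 20 points | 12 / 12 | 18.9 v 18.6 |
| 10 points | 8 / 0 | 8.4 v 10.1 |
| 10 points | 8 / 8 | 9.6 v 9.5 |

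In the equal-SD rows, rates are truncated at 1%, which lowers the true difference. A second set (baselines 10-15%, SD of change larger in Full Support, 300 patients per clinic, r from 0 to 0.7) gave -10% to -24%. With a 30% baseline rising to 40% and Self-Guided SD 0, the bias was about -3%; from 40% to 50% it was nil. For a metric that should fall (terminal digit zero, metric 8), drops from 30% to 20% or from 40% to 25% gave an effect 4-5% too large.

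Primary outcome (65.6% baseline, Full Support SD 4.4): -0.2% to +3.1% of the effect. The largest case was 7.01 v 6.80, or 0.2 points.

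**3. Zero-variance strata.** With Table 3 categories there are 3 × 2 × 5 = 30 strata per clinic, or 600 for 20 clinics. Var is zero when the cell is at 0% or 100% at each time. One patient at both times always meets this. For n patients at each time and independent draws at level p, the chance is [pⁿ + (1-p)ⁿ]²:
- p = 0.656: n = 2, 30%; n = 3, 10%; n = 5, 1.6%.
- p = 0.12: n = 5, 28%; n = 10, 7.8%.

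Take an assumed race mix of 45/30/20/2/3%, an age mix of 15/50/35% and equal sexes. At 1,000 patients the smallest cell then expects 1,000 × 0.02 × 0.15 × 0.5 = 1.5 patients. With control at 66% and then 69%, about 30 of the 600 cells have zero variance if stratum sizes are drawn separately at the two times, and about 47 if the size is the same at both. At 300 to 2,000 patients per clinic, at least one such cell appeared in essentially every simulated trial.

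A separate simulation with uneven strata gave, at 300, 1,000 and 3,000 patients, 16-18%, 6-7% and 0.6-0.9% of non-empty cells at 65.6% control, and 27-33%, 14-17% and 4-5% for a 12% metric. The chance of at least one was 99-100% throughout. At 10,000 patients it was 1-3% and 61-88%. With equal-sized strata and 1,000 patients it was 0% and 24%.

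These draws treat the two times as independent. In the plan's own example the baseline and 6-month periods share January to May 2019, and earlier months share more. A cell at a boundary is therefore likelier to stay there than the simulation allows.

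**The case against.** The strongest reply is that little depends on this. The three primary tests are essentially unaffected, secondary outcomes are called exploratory, and the stratified model is one the plan will only consider. Step 3 says approximated and writes no formula, so site-level p(1-p) is an inference. Clinic sizes, stratum definitions and process-metric levels are all absent, so every frequency above rests on assumptions. A zero variance would also be obvious at fitting rather than a silent bias. All of this stands, and it limits the weight of the point. It does not remove it: the text names the time-specific level as an input and carries the weights into strata with no safeguard, so the rule would have to be repaired after the data are seen.

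Three stronger readings are tempting and are not supported:
- That process-measure effects are attenuated as a matter of course. The bias nearly vanishes with equal SDs or baselines of about 30% or more, and it reverses for metric 8. Tailored facilitation in one arm makes unequal variation plausible, but the documents do not show it.
- That the bias feeds the mediation analysis. That section specifies nested regressions on clinic-level pre-post differences, with mediator changes entered as clinic values. It mentions no weights and does not use the weighted process effects.
- That every sparse stratum gets an infinite weight, or that p(1-p) governs every metric. A boundary value at one time only leaves a finite weight, and metric 7 is a mean in mmHg.

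**Conclusion.** The concern holds in a limited form. For percentage metrics the follow-up result helps set its own weight. The consequence is about 0.2 points or less for the primary outcome. It is a conditional bias of roughly 10-24% toward a smaller effect for process metrics with assumed baselines of 10-15% and more variable change under Full Support.

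The firmer defect is the stratified mixed model. If the strata follow Table 3 and are uneven in size, at least one infinite weight is almost certain at 300-2,000 patients per clinic, and one is enough to stop the model. With very large clinics or evenly filled strata the problem can be rare or absent for the control metric. The primary comparison is not in doubt.

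**What to change.** Write one formula and use it in both step 3 and the Sensitivity analyses paragraph. For percentage metrics, take the site or stratum sample sizes at the two times (the metric's own denominators) and a single level p̄ pooled across clinics and arms:

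Var = p̄(1-p̄) × [1/n0 + 1/n6 - 2r/√(n0·n6)],

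with n at month i in place of n6 for the monthly model. The factor p̄(1-p̄) is common to all sites and cancels when the weights are normalized, so no site's own follow-up result sets its weight. With r below 1 and p̄ strictly between 0 and 1, every non-empty cell has positive variance. In the first example above all weights become equal and the mean change returns to 7.5 points. In the simulations, weights from n alone gave 20.1 and 10.1, in line with the true values.

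Also state that strata empty at either time are omitted, define the strata, and for metric 7 use the sample sizes with a pooled SD.

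Weights from the baseline level alone would also remove the dependence on the outcome, but would still need smoothing in small strata.

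The cost is a wording change with no new data. The weights become slightly less exact where true levels differ widely between clinics. The primary result would be essentially unchanged.
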